Rate	A measure of event occurrence, calculated by dividing the total number of events by the total amount of person-time within an exposure category
Risk	The proportion of a fixed cohort in which an outcome occurs during a specified period of time
Start of data collection	Date from which information on the first study subject is first recorded in the study dataset

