**Study Size:**

This study aims to include patients who have been or are currently being treated with idelalisib according to the product information and treatment guidelines in routine clinical practice for the treatment of refractory FL, after marketing authorisation in the EU (September 2014) and Australia (January 2015).

Assuming a median treatment period of 8 months, a retrospective timeframe of around 3 years and a prospective observation period of 2.5 years, it is expected that data of approximately 300 patient-years will be collected.

Patients will be identified and enrolled in Europe (pending outcome of study feasibility: Australia, Austria, Belgium, France, Germany, Greece, Ireland, Italy, Portugal, Spain, Sweden, Switzerland and the United Kingdom) and Australia.

---

**Data Analysis:** Continuous variables will be summarized by mean, standard deviation, median, lower quartile, upper quartile, minimum and maximum. Categorical variables will be summarized by number and percentage of patients in each categorical definition including 95% confidence intervals.

Multivariate Poisson regression analyses will be used to estimate adjusted rates of ADRs and SADR.

Multivariate Cox Proportional Hazard analyses will be used to model time-to-event data, and time to ADRs and SADR.

Kaplan Meier will be used to illustrate time-to-event analyses.

Stratified analyses will be used to account for potential behavioral changes of the site staff after the initiation of the study that might introduce bias between retrospective and prospective data collection.

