## **9. RESEARCH METHODS**

### **9.1. Study Design**

A retrospective cohort study enrolling patients who were or are being treated with idelalisib for refractory FL according to the product information and treatment guidelines in routine clinical practice after the country specific approval date.

Patient's data will be collected from the date of treatment initiation with idelalisib until 6 months after treatment discontinuation.

The study design allows for both retrospective and prospective data to be collected. The start of data collection is defined as the entry of the first patient into the eCRF. In the data analysis, any data prior to the start of the study will be considered retrospective. Any data after that date will be considered prospective.

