#### Discontinuation (as defined by stopping treatment for more than 30 days) information

- Date and reason for discontinuation
- In case of death:
  - Date and cause of death

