### **9.5. Study Size**

This study aims to include patients who have been or are currently being treated with idelalisib according to the product information and treatment guidelines for the treatment of refractory FL after marketing authorization in the EU (September 2014) and Australia (January 2015).

Prevalence data for iNHL in the EU are limited. HAEMACARE, a European cancer registry-based project on hematologic malignancies funded by the European Commission, provides European incidence rates but not prevalence data {Sant 2010}. Australian prevalence data could not be identified. The Decision Resources Group (<http://www.decisionresourcesgateway.com/index.aspx>) estimated a 10-year limited-duration prevalence for FL in 5 major EU countries (France, Germany, Italy, Spain, and United Kingdom) over the 2011-2021 forecast period based on cancer registry databases in the EU-5. The EU prevalence estimates for FL ranged from 1.4 (Spain) in 2011 to 3.1 (France) per 10,000 in 2015 (RMP, section 1.1.1.4.2).

Based on the pivotal studies 101-09, GS-US-313-0124 and GS-US-313-0125 the median treatment period is estimated to be 8 months, taking into account that studies GS-US-313-0124 and GS-US-313-0125 were terminated early. Thus, a retrospective timeframe of around 3 years and a prospective observation period of another 2.5 years allow data of approximately 300 patient-years to be collected.

A sample size of 300 patient-years is based on the chance to find a proportion of adverse events of 3.2% with a precision of 2%. The table below shows the relationship between various detectable single proportions of AEs and precision of the estimate.

Proportions found in studies 101-09, GS-US-313-0124 and GS-US-313-0125 were 1.4% ( Grade 3 diarrhea and/or colitis), 2.0% (( Grade 3 febrile neutropenia), 6.1% (( Grade 3 infection) and 8.1% (( Grade 3 rash).

Proportion of AEs	3.2%	5.2%	7.6%
Precision	0.02	0.025	0.03

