## 9.7. Data Analysis

Categorical variables will be summarized descriptively by number and percentage of patients in each categorical definition including 95% confidence intervals. Continuous variables will be summarized descriptively by mean, standard deviation, median, lower quartile, upper quartile, minimum and maximum.

Multivariate Poisson regression analyses will be used to estimate rates of ADRs and SADR, adjusted for potential confounders (demographics, baseline disease assessment, medical history, treatment history, treatment changes; see section 9.3).

Multivariate Cox Proportional Hazard analyses will be used to model time-to-event data, and time to ADRs, SADR and AESIs.

Kaplan Meier curves will be used to illustrate time-to-event analyses.

Special focus will be given to the differences in retrospective and prospective data collection. Although not by intention, data might be collected differently in retrospect compared to patient's data that will be collected prospectively. Retrospective patients will be recruited through systematic search of the sites' patient data management system, whereas prospective data will be collected from those patients prescribed idelalisib after the start of the study. Behavioral changes of the site staff after the initiation of the study might play a role in differential data collection. Thus, missing data for the retrospective data might be an issue. Stratified analyses will be conducted to account for this potential bias.

The extent of missing data in the study will be described and tabulated. Imputation methods will be used to account for missing values in the dataset for those variables used in multivariate modeling (demographics, baseline disease assessment, medical history, treatment history) and changes in idelalisib treatment following the current ENCePP guidelines (Methodological Standards in Pharmacoepidemiology: Section 5.3. Handling of missing data;

[http://www.encepp.eu/standards\\_and\\_guidances/methodologicalGuide5\\_3.shtml](http://www.encepp.eu/standards_and_guidances/methodologicalGuide5_3.shtml) {Rubin 1987}, {Moons 2006}, {Welch 2014}. Multiple imputation by chained equations (MICE) as sequential regression multiple imputation will be used handling of missing data {Azur 2011}. Using MICE, missing values are imputed based on the observed values for a given individual and the relationships within the data for other participants.

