3.1 Is the study design described? (e.g. cohort, case-control, cross-sectional, new or alternative design)				9.1
3.2 Does the protocol specify whether the study is based on primary, secondary or combined data collection?				9.3
3.3 Does the protocol specify measures of occurrence? (e.g. incidence rate, absolute risk)				9.7
3.4 Does the protocol specify measure(s) of association? (e.g. relative risk, odds ratio, excess risk, incidence rate ratio, hazard ratio, number needed to harm (NNH) per year)				-
3.5 Does the protocol describe the approach for the collection and reporting of adverse events/adverse reactions? (e.g. adverse events that will not be collected in case of primary data collection)				9, 11

Comments:

Only incidence rates (crude and adjusted) will be calculated. No comparisons will be made

Section 4: Source and study populations	Yes	No	N/A	Section Number
4.1 Is the source population described?				9.2
4.2 Is the planned study population defined in terms of:				
4.2.1 Study time period?				6
4.2.2 Age and sex?				-
4.2.3 Country of origin?				9.2
4.2.4 Disease/indication?				9.2
4.2.5 Duration of follow-up?				9.1
4.3 Does the protocol define how the study population will be sampled from the source population? (e.g. event or inclusion/exclusion criteria)				9.2

Comments:

Results will distinguish for age and sex. But the population will not be specifically defined for both characteristics.

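### Kaplan-Meier curves for time to ADRs, SADRs and AESIs overstate risk if deaths are censored and the curve is read as risk; cumulative incidence curves suit these outcomes better

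*Protocol*

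**What the plan says.** Protocol section 9.7 states: "Multivariate Cox Proportional Hazard analyses will be used to model time-to-event data, and time to ADRs, SADR and AESIs". The next sentence fixes the display: "Kaplan Meier curves will be used to illustrate time-to-event analyses". The Data Analysis entry of the synopsis (section 4) repeats it: "Kaplan Meier will be used to illustrate time-to-event analyses". The protocol names no cumulative incidence function and mentions no competing event.

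Other places bear on the point:

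- Section 9.1, on follow-up: "Patient's data will be collected from the date of treatment initiation with idelalisib until 6 months after treatment discontinuation".
- Section 9.5, on treatment duration: "the median treatment period is estimated to be 8 months".
- Section 9.3, among the discontinuation items: "Date and cause of death".
- Section 9.9 explains that deceased patients enter without consent so that the cohort is not tilted towards survivors and the risk of death is not understated.
- Section 2 (glossary) defines risk as: "The proportion of a fixed cohort in which an outcome occurs during a specified period of time".
- Annex 1, comment under the study design items, on measures of occurrence: "Only incidence rates (crude and adjusted) will be calculated. No comparisons will be made".

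**The concern.** A patient who dies cannot later develop colitis, pneumonitis, PJP or CMV infection. Kaplan-Meier with deaths censored treats that patient as still able to have the event, at the same rate as those who remain under observation. The resulting 1-KM describes a setting in which nobody dies. It is not the share of the treated cohort that has the event, which is the quantity the glossary calls risk.

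Deaths will fall inside the observation window. The protocol records them, includes deceased patients on purpose, and follows patients for 6 months after treatment stops. The study exists to describe the safety profile to a regulator, and a curve of time to a safety event is easily read as absolute risk. The error runs in one direction and does not shrink as the sample grows.

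**Working it through.** **1. The plan's own figures.** The protocol states no cumulative risk and no death rate. The nearest figure that can be checked is the precision table in section 9.5, used here as a yardstick. The 95% half-width is 1.96 × √(p(1−p)/n), with n = 300. The protocol states 300 in patient-years; the formula takes it as a number of patients.

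| Proportion p | Half-width at n = 300 | Stated precision | n required |
|---|---|---|---|
| 3.2% | 0.0199 | 0.02 | 298 |
| 5.2% | 0.0251 | 0.025 | 303 |
| 7.6% | 0.0300 | 0.03 | 300 |

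All three columns reproduce.

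**2. Inputs for the curve.**

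- Horizon: 8 months median treatment (section 9.5) plus 6 months (section 9.1) gives 14 months, T = 14/12 years.
- Event proportions: 1.4% to 8.1%, the range of earlier-study figures in section 9.5, taken as the true cumulative incidence.
- Mortality: not in the documents. Assumed one-year death probability of 5%, 10%, 20% or 30%.
- Constant hazards, also assumed.

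**3. Formulas.** Let h be the event hazard and d the death hazard, with d = −ln(1 − one-year death probability).

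- Cumulative incidence: F(T) = h/(h+d) × (1 − exp(−(h+d)T))
- Kaplan-Meier with deaths censored: 1-KM(T) = 1 − exp(−hT)

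For each case, h is solved so that F(T) equals the true proportion, and 1-KM is then calculated from that h.

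**4. One case in full.** True risk 8.1%, yearly mortality 20%. d = −ln(0.80) = 0.2231. Solving F(14/12) = 0.081 gives h = 0.0825. Then 1-KM = 1 − exp(−0.0825 × 1.1667) = 9.18%. The excess is 1.08 points, a ratio of 1.13.

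**5. Results at 14 months: 1-KM (excess in points).**

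| True risk | 5% mortality | 10% | 20% | 30% |
|---|---|---|---|---|
| 1.4% | 1.44% (0.04) | 1.49% (0.09) | 1.59% (0.19) | 1.71% (0.31) |
| 3.2% | 3.30% (0.10) | 3.40% (0.20) | 3.63% (0.43) | 3.91% (0.71) |
| 6.1% | 6.28% (0.18) | 6.48% (0.38) | 6.92% (0.82) | 7.44% (1.34) |
| 8.1% | 8.34% (0.24) | 8.60% (0.50) | 9.18% (1.08) | 9.87% (1.77) |
| 20% (assumed) | 20.58% (0.58) | 21.20% (1.20) | 22.59% (2.59) | 24.22% (4.22) |

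The relative excess is about 3%, 6%, 13% and 22% across the four mortality levels. At 8 months it is about 2%, 3.5%, 7.5% and 12%.

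**6. Cross-check.** A simulation of 400,000 patients with 20% yearly mortality, an event hazard of 0.08 per year and censoring 6 months after discontinuation gave 8.9% by Kaplan-Meier and 7.9% by Aalen-Johansen at 14 months. The formulas give 8.9% and 7.9%.

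**The case against.** The strongest reply is that the curves only illustrate. Section 9.7 also plans numbers and percentages of patients with 95% confidence intervals, section 8 plans event rates, and Annex 1 gives crude and adjusted incidence rates as the measures of occurrence. None of these is inflated by deaths in this way, and neither are Cox hazards read as cause-specific. This stands. A reader might infer that the curves are the plan's only absolute-risk output, or that the study's reported risks will be overstated; the protocol supports neither.

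The protocol also does not say that deaths are censored, that 1-KM will be shown, or which outcomes get a curve. Such details may sit in the statistical analysis plan. This stands in part: the bias is conditional on those choices. But the protocol names the estimator, and an analysis plan that follows it would produce Kaplan-Meier curves for these outcomes.

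Not every death competes. Death is a criterion for an SAE (section 11.3.2), and a SADR is a causally related SAE (section 11.3.5), so a drug-related death is itself a SADR. For SADRs only the remaining deaths compete, and the table above is then an upper figure for a given total mortality.

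Finally, the excess for the quoted proportions is below the planned precision in every case tried. This also stands and limits the severity. It passes 2 points only for a commoner event: at an assumed 20% risk, from about 20% yearly mortality. Even there, 4.22 points at 30% mortality is just under that event's own half-width at n = 300, 1.96 × √(0.20 × 0.80/300) = 4.5 points.

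**Conclusion.** The point holds in conditional form. Where deaths are censored and the curve is read as risk, the named method overstates the proportion of patients who have the event. The overstatement is roughly 3% to 22% in relative terms at about 14 months, or 0.04 to 1.77 points for proportions of 1.4% to 8.1%. These sizes rest on constant hazards and an assumed yearly mortality of 5% to 30%; the direction does not depend on the mortality chosen.

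Two stronger readings are not supported. One is that death is a frequent competing event: section 9.9 shows that deaths are expected, but no passage says how many. The other is that comparison of retrospective with prospective data will be distorted. That would need mortality to differ between the two, and nothing in the protocol documents such a difference.

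Severity is minor to moderate: a better-suited estimator is available at almost no cost, but the main planned outputs are unaffected.

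**What to change.** In section 9.7 and in the Data Analysis entry of the synopsis:

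- For ADRs, SADRs and AESIs/HOIs, name Aalen-Johansen cumulative incidence curves with 95% confidence intervals, with death as the competing event. For SADRs, count as competing only those deaths that are not themselves SADRs.
- Keep Kaplan-Meier for all-cause death.
- Label the Cox results as cause-specific hazards.
- Use one term for the outcomes of special interest: section 9.7 says AESIs without defining it, while the rest of the protocol says HOIs.

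The cost is a change of wording and the use of standard software. No new data are needed, because date and cause of death are already collected.

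### The Poisson rate model omits time since first dose, so retrospective and prospective rates can differ, in a direction that depends on which stratum definition applies, even when documentation is equal

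*Protocol*

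**What the plan says.** The glossary (Section 2) defines a rate as a quantity "calculated by dividing the total number of events by the total amount of person-time within an exposure category". Section 9.7 states: "Multivariate Poisson regression analyses will be used to estimate rates of ADRs and SADR, adjusted for potential confounders", and gives the confounder groups as "demographics, baseline disease assessment, medical history, treatment history, treatment changes; see section 9.3". Time since first dose is not among them. Treatment changes are, but a dose change or interruption does not measure time on drug.

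The same section adds that "Multivariate Cox Proportional Hazard analyses will be used to model time-to-event data, and time to ADRs, SADR and AESIs", with Kaplan-Meier curves. On possible differences in recording it states: "Special focus will be given to the differences in retrospective and prospective data collection", and then: "Stratified analyses will be conducted to account for this potential bias". The synopsis and Section 9.9 return to the same idea.

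The strata are described in two ways. Section 9.1 splits by calendar date: "In the data analysis, any data prior to the start of the study will be considered retrospective", and later data count as prospective, so one patient can contribute to both strata. Section 9.7 instead describes prospective data as coming from patients prescribed idelalisib once the study has begun, which assigns whole patients to a stratum. Annex 1 (Section 3, comments) says that only crude and adjusted incidence rates will be produced, without comparisons.

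**The concern.** A rate without a time-on-treatment term is an average over whatever mix of early and later treatment time the stratum contains. Under the calendar split, the retrospective stratum begins with no users at approval and is rich in first-months time. The prospective stratum also receives the later time of patients already on drug at study start, who have come through their first months. Under the patient-level description the imbalance runs the other way. Earlier patients are followed longer, whereas later patients can be cut off by the end of data collection and so contribute proportionally more early time.

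The stratified rates are the analysis that Section 9.7 names for uneven documentation. If time on treatment also moves those rates, similar strata do not show that old charts are complete, and different strata do not show that they are deficient.

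**Working it through.** **Plan's own figures.** The protocol gives no number for this contrast. Its study size reproduces from n = 1.96² × p(1−p)/d²: 297.5 (3.2%, 0.02), 303.0 (5.2%, 0.025) and 299.7 (7.6%, 0.03). The formula yields 300 patients; Section 9.5 labels the figure patient-years. It is used below only to gauge event counts.

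**Inputs from the protocol.** Median treatment period 8 months (Section 9.5). Retrospective window R ≈ 40 months, from EU authorisation in September 2014 to Q1 2018. Prospective window P ≈ 31 months, from Q1 2018 to Q3 2020 (Sections 6 and 9.5).

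**Assumptions not in the protocol.** Exponential treatment duration; uniform starts within each window; start rate after study start equal to r = 1, 0.5 or 0.25 times the earlier rate; early = first 3 months; early:later event-rate ratio h; on-treatment time only; identical documentation in both strata.

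**Step 1, person-time.** λ = ln 2/8, so 1/λ = 11.54 months and 1/λ² = 133.2. With one start per month over T months, expected time spent in the first a months of treatment is

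A(T,a) = (T/λ)(1−e^(−λa)) − (1/λ²)[1 − e^(−λa)(1+λa)].

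- Before study start: early A(40,3) = 101.88; total A(40,40) = 332.62.
- New starters after study start: early A(31,3) = 78.10; total A(31,31) = 233.66.
- Patients on drug at study start, time after that date: total (1/λ)²(1−e^(−40λ))(1−e^(−31λ)) = 120.25; early part (1/λ²)[1 − e^(−3λ)(1+3λ)] = 3.79.

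**Step 2, early shares under the date split (Section 9.1).**

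- Retrospective: a = 101.88/332.62 = 0.306.
- Prospective: b = (78.10r + 3.79)/(233.66r + 120.25) = 0.231, 0.181 and 0.131 for r = 1, 0.5 and 0.25.

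**Step 3, early shares under the patient split (Section 9.7).**

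- Retrospective: (101.88 + 3.79)/(332.62 + 120.25) = 0.233.
- Prospective: 78.10/233.66 = 0.334. This does not depend on r.

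**Step 4, retrospective/prospective rate ratio.** Ratio = [1 + (h−1)a]/[1 + (h−1)b].

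| Split | h = 1 | h = 2 | h = 3 | h = 5 |
|---|---|---|---|---|
| Date, r = 1 | 1.00 | 1.06 | 1.10 | 1.16 |
| Date, r = 0.5 | 1.00 | 1.11 | 1.18 | 1.29 |
| Date, r = 0.25 | 1.00 | 1.16 | 1.28 | 1.46 |
| Patient, any r | 1.00 | 0.92 | 0.88 | 0.83 |

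For the date split at h = 3, the retrospective under-recording that would be exactly cancelled is 1 − 1/ratio: 9%, 16% and 22%. For the patient split at h = 3, the apparent under-recording where none exists is 1 − 0.88 = 12%.

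**Step 5, sensitivity at h = 3.**

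- Section 9.5's rounder windows (36 and 30 months) plus the 6-month follow-up after discontinuation: date split 1.11, 1.18 and 1.26; patient split (1 + 2×0.175)/(1 + 2×0.265) = 0.88.
- Same windows and follow-up, early = 6 months: date split 1.14 (r = 1) and 1.25 (r = 0.5); patient split (1 + 2×0.351)/(1 + 2×0.503) = 0.85.
- Same windows and follow-up, early = 3 months, enrolment ending 12 months into the prospective period: patient split (1 + 2×0.176)/(1 + 2×0.200) = 0.97. The patient-split artefact therefore comes largely from cut-off at the end of data collection.

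**The case against.** Several counter-arguments have force.

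- **No formal comparison is planned.** A reader might infer that the plan fits one constant rate and tests it between strata. It does not say so: no stratum ratio, test or decision rule appears, Annex 1 disclaims comparisons, and the glossary entry is a general definition. What stands is that Section 9.7 puts special weight on this difference and offers stratification as the answer, so the two rates will be read side by side.
- **Time bands belong in the SAP.** An SAP that is not shown may add them, and their absence alone would be no finding. The point is narrower: the stated covariate list and the stratum definitions together produce the imbalance, and the two definitions conflict within the protocol.
- **Stratification is not the only safeguard.** It would be wrong to call it that. Abstractor training, a common eCRF, automatic checks, queries, remote monitoring and tabulation of missing data are all planned (Sections 9.4 and 9.7 to 9.9). These act mainly on data capture. The planned imputation covers model variables and treatment changes, not events that were never recorded.
- **Cox and Kaplan-Meier analyses can use time since first dose.** They can, so time on treatment is not ignored throughout. They do not alter the stratified rates, and under the date split they need delayed entry for patients already on drug.
- **Sampling error is larger.** Applying the proportions in Section 9.5 to 300 patients gives about 4 (1.4%) to 24 (8.1%) patients with an event. With events split 56:44, the 95% limits for a stratum ratio span a factor of about 2.2 to 6.9 either way. A shift of 1.10 to 1.28 lies well inside that for single outcomes. This limits the practical weight, but it does not make the contrast interpretable.

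**Conclusion.** The concern holds in a limited form. As listed, the rate model does not adjust for time on treatment, and the strata differ in their early-time share under either definition. At h = 3 with a 3-month early window, the artefact is a ratio of about 1.10 to 1.28 under the date split and about 0.88 under the patient split.

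The size rests on assumed values of h, accrual pattern and exponential duration; the protocol gives no event timing, and a constant hazard removes the problem. A reader might infer that the effect always hides under-recording. The documents do not support that, because the sign depends on a definition that Sections 9.1 and 9.7 leave in conflict. Nor do they support saying that the pooled rate can never be set beside other studies; it needs the follow-up mix stated alongside it. This is a worthwhile correction to one part of the analysis and not a flaw in the whole plan.

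**What to change.** 1. Reconcile Sections 9.1 and 9.7 to a single definition of retrospective and prospective data. This comes first, because it sets the direction of the problem.
2. In Section 9.7, split person-time by time since first dose in the Poisson model. Use few bands, for example 0–3, >3–6 and >6 months on treatment, with post-treatment time kept separate.
3. Report retrospective and prospective rates within bands, or as one contrast adjusted for band where events are few.
4. If the date split is kept, state that Cox and Kaplan-Meier analyses of prospective data use delayed entry at each patient's time on treatment at study start.

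No new data are needed: idelalisib start, dose-change and discontinuation dates are already in Section 9.3, and event dates are needed for the planned time-to-event analyses. The cost is a little more programming and wider intervals within bands. For the rarer outcomes, counts per band will be very small, so the band-adjusted contrast is the more realistic report there.

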Stratified analyses will be taken into consideration to account for potential behavioral changes of the site staff after the initiation of the study that might introduce bias between retrospective and prospective data collection. These stratified analyses also account for the fact that less documentation might be available in data collected retrospectively.

Patterns of missing data will be determined using the methodology outlined by Chen {Chen 1999}. Here, it has to be determined if the "Missing At Random" (MAR) criterion is fulfilled. If the assumptions of MAR or missing completely at random (MCAR) are met then a multiple imputation approach will be used. If this assumption doesn't hold, a full case or regression approach may be used.

Multiple imputation by chained equations (MICE) also referred to as sequential regression multiple imputation, is a validated statistical method for the handling of missing data {Azur 2011}. Using MICE, missing values are imputed based on the observed values for a given individual and the relationships within the data for other participants.

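### Stratifying by retrospective and prospective data can describe under-documentation but cannot account for it, and for single named outcomes similar-looking strata would not show that capture was complete

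*Protocol*

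**What the plan says.** Section 9.7 accepts that data may be collected differently in retrospect, that site behaviour may change once the study starts, and that retrospective data may be missing. Its answer is "Stratified analyses will be conducted to account for this potential bias". Section 9.9 opens more softly ("Stratified analyses will be taken into consideration to account for potential behavioral changes of the site staff") but then states the property outright: "These stratified analyses also account for the fact that less documentation might be available in data collected retrospectively".

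Other provisions bear on whether anything else closes the gap:

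- **Source (9.4).** The medical record is the primary source, and the safety information collected is what was entered there.
- **Imputation (9.7).** It covers the covariates of the multivariable models and changes in idelalisib treatment.
- **Adjustment (9.7).** The confounders listed for the Poisson models do not include the mode of data collection.
- **Source verification (9.10.1.1, 10.3).** Data without patient consent are monitored remotely with no source verification. Patients identified retrospectively are generally not asked for consent.
- **Size (9.5).** The 300 patient-years and the precision table refer to all data together.

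**The concern.** The protocol presents stratification as a safeguard against lost events. Splitting the data into two strata changes how the counts are shown but not what they contain. If events are missing from the retrospective count, that stratum's rate is low, and so is any rate that pools it with the other. Imputation does not help, because an event that nobody wrote down is not a missing cell in a known row. The data most exposed to the problem also get the least checking against source.

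The study was required in order to describe harm in this population better, so the direction matters: lost events make idelalisib look safer. A report that shows two similar strata and cites the protocol's wording could present the bias as dealt with when it has been neither measured nor removed.

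**Working it through.** **Inputs**

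- Planned information, section 9.5: "a retrospective timeframe of around 3 years and a prospective observation period of another 2.5 years allow data of approximately 300 patient-years".
- Outcome proportions, section 9.5: 1.4%, 2.0%, 6.1% (grade 3 infection) and 8.1% (grade 3 rash).
- Retrospective share of person-time: 3/(3 + 2.5) = 0.545. This assumes that person-time follows calendar time; it is varied from 0.50 to 0.70.
- Loss of events in retrospective data: 30%. This is an assumption; the protocol gives no figure.

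**1. The protocol's own size.** With n = 1.96² × p(1 − p)/d²:

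- p = 3.2%, d = 0.02: 298
- p = 5.2%, d = 0.025: 303
- p = 7.6%, d = 0.03: 300

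The figure of 300 is reproduced, and it rests on the pooled data.

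**2. Bias of the pooled rate.** Relative bias = −(retrospective share × loss).

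- Share 0.545: 0.545 × 0.30 = 0.164, so about 16% low.
- Share 0.50: 15% low. Share 0.70: 21% low.
- For rash, 8.1% would be seen as 8.1 × (1 − 0.164) = 6.8%. For infection, 6.1% would be seen as 5.1%.

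Stratifying enters nowhere in this formula.

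**3. What the two strata could show.** Expected events with full capture are 0.061 × 300 = 18.3 and 0.081 × 300 = 24.3. The interval is RR × exp(±1.96 × √(1/a + 1/b)), where a and b are the retrospective and prospective counts.

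| Outcome | a (after 30% loss) | b | True ratio | Approx. 95% CI |
|---|---|---|---|---|
| Grade 3 rash | 24.3 × 0.545 × 0.7 = 9.3 | 24.3 × 0.455 = 11.0 | 0.70 | 0.29 to 1.68 |
| Grade 3 infection | 18.3 × 0.545 × 0.7 = 7.0 | 18.3 × 0.455 = 8.3 | 0.70 | 0.26 to 1.91 |

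Both intervals include full capture (1.0) and a loss of well over half.

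Power expresses the same thing. An exact conditional comparison at two-sided 5% would detect the 30% loss 7% of the time for infection and 9% for rash if the smaller tail is doubled, or 9% and 11% with the minimum-likelihood p-value. For the 1.4% and 2.0% outcomes it is below 5% either way. About 249 observed events would be needed for 80% power.

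**4. Denominator.** Section 9.5 applies proportions of patients to patient-years. With a median treatment period of 8 months, 300 patient-years corresponds to 300/(8/12) = 450 patients on treatment time alone, or 300/(8/12 + 0.5) = 257 with the six months of follow-up. Over 257 to 450 units and shares of 40% to 70%, power for any single named outcome stays at or below about 20%, even with less conservative tests.

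**5. What a capture table would show.** Corrected pooled rate = (a/capture + b)/300. For rash with a = 9.3 and b = 11.0 (unrounded values used):

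| Assumed capture | Corrected events | Corrected rate |
|---|---|---|
| 100% | 20.3 | 6.8% |
| 85% | 22.0 | 7.3% |
| 70% | 24.3 | 8.1% |
| 50% | 29.6 | 9.9% |

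**The case against.** **No between-strata test is planned.** The comments in Annex 1 say that the study has no hypothesis testing and that no comparisons will be made. That stands: the plan cannot be faulted for an underpowered test it does not contain. The interval in step 3 still matters, because it limits what anyone may conclude from seeing the two rates side by side.

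**The named outcomes are not the whole objective.** A reader might infer that the strata are uninformative for the entire safety profile. The protocol does not support that. It gives no rate for all SAEs or ADRs. At about one event per patient-year (300 events with full capture), power to show a 30% loss would be about 79%, ignoring overdispersion from repeat events.

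**The loss is assumed.** This also stands. Both periods use medical records with the same variables, and the focus is on serious and mostly grade 3 events, which are more likely to be charted. The protocol says only that documentation may be poorer.

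**The plan is open about the limitation.** It lists information bias and missing values, tabulates missing data and schedules an interim report on retrospective data. Reporting by stratum is an ordinary way to expose differential collection. That supports keeping the stratified analysis, but not the statement that it accounts for the loss.

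**The prospective rate as the reference.** A reader might infer that the prospective rate is the unbiased answer. The protocol does not support this. Patients identified prospectively give consent, whereas deceased and retrospectively identified patients generally do not (9.9, 10.3). Section 7.1 describes new warnings and risk-minimisation measures, so true rates may differ by period. With 300 × 2.5/5.5 = 136 units, the half-width at 3.2% also grows from 0.020 to 0.030.

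**Detail for the analysis plan.** The form of a bias table could be left there. The claim in 9.7 and 9.9 could not, because the protocol itself makes it.

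**Conclusion.** The point holds in a limited form. Sections 9.7 and 9.9 credit stratification with a property it lacks, and no other provision in the protocol restores uncharted events. Any pooled rate remains low by share × loss: about 16% for a 30% loss at a share of 3/5.5, and 15% to 21% for shares of 50% to 70%. The formula is exact if the true rate is the same in both periods. The 30% is illustrative, and the share rests on person-time following calendar time.

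For individual named outcomes, the strata are too sparse to reveal a loss of that size, so similar rates must not be read as complete capture.

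The documents do not show that the pooled rates will in fact be low by any given amount. The softer verb in the opening sentence of section 9.9, compared with 9.7, is an editorial inconsistency and carries no weight here.

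**What to change.** 1. In sections 9.7 and 9.9, say that the stratified analyses *describe* differences between retrospective and prospective data, in place of *account for*.
2. Report the retrospective rate, the prospective rate and their ratio with a 95% CI beside the pooled rate. State that the ratio also reflects calendar time, changes in risk minimisation and consent-based selection, and that similar strata do not show complete capture.
3. Add a bias table that divides the retrospective event count by assumed capture of 100%, 85%, 70% and 50% and shows the corrected pooled rate, as in step 5.
4. Do not name the prospective rate as the reference estimate.

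The cost is a change of wording, one extra table and a visibly wider range around the pooled rate. No additional data are needed.
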